16.3.3.4 Evaluation of response

Timepoint Response (Overall Response)

It is assumed that at each protocol-specified timepoint, a response assessment occurs. [Table 1](#) provides a summary of the overall response status calculation at each timepoint for patients who have measurable disease at baseline.

When patients have non-measurable (therefore nontarget) disease only, [Table 2](#) is to be used.

Table 1 Timepoint Response: Patients with Target Lesions (with or without Nontarget Lesions)

Target Lesions	Nontarget Lesions	New Lesions	Overall Response
CR	CR	No	CR
CR	Non-CR/non-PD	No	PR
CR	Not evaluated	No	PR
PR	Non-PD or not all evaluated	No	PR
SD	Non-PD or not all evaluated	No	SD
Not all evaluated	Non-PD	No	NE
PD	Any	Yes or no	PD
Any	PD	Yes or no	PD
Any	Any	Yes	PD

CR= complete response; NE= not evaluable; PD = progressive disease; PR= partial response; SD = stable disease.

Table 2 Timepoint Response: Patients with Nontarget Lesions Only

Nontarget Lesions	New Lesions	Overall Response
CR	No	CR
Non-CR/non-PD	No	Non-CR/non-PD ^a
Not all evaluated	No	NE
Unequivocal PD	Yes or no	PD
Any	Yes	PD

CR= complete response; NE= not evaluable; PD = progressive disease.

^a “Non-CR/non-PD” is preferred over “stable disease” for nontarget disease since stable disease is increasingly used as an endpoint for assessment of efficacy in some trials; thus, assigning “stable disease” when no lesions can be measured is not advised.

Missing Assessments and Not-Evaluable Designation

When no imaging/measurement is done at all at a particular timepoint, the patient is not evaluable at that timepoint. If only a subset of lesion measurements are made at an

assessment, usually the case is also considered not evaluable at that timepoint, unless a convincing argument can be made that the contribution of the individual missing lesion(s) would not change the assigned timepoint response. This would be most likely to happen in the case of PD. For example, if a patient had a baseline sum of 50 mm with three measured lesions and, during the study, only two lesions were assessed, but those gave a sum of 80 mm, the patient will have achieved PD status, regardless of the contribution of the missing lesion.

If one or more target lesions were not assessed either because the scan was not done or the scan could not be assessed because of poor image quality or obstructed view, the response for target lesions should be “unable to assess” since the patient is not evaluable. Similarly, if one or more nontarget lesions are not assessed, the response for nontarget lesions should be “unable to assess” except where there is clear progression. Overall response would be “unable to assess” if either the target response or the nontarget response is “unable to assess,” except where this is clear evidence of progression as this equates with the case being not evaluable at that timepoint.

Table 3 Best Overall Response When Confirmation Is Required

Overall Response at First Timepoint	Overall Response at Subsequent Timepoint	Best Overall Response
CR	CR	CR
CR	PR	SD, PD, or PR ^a
CR	SD	SD, provided minimum duration for SD was met; otherwise, PD
CR	PD	SD, provided minimum duration for SD was met; otherwise, PD
CR	NE	SD, provided minimum duration for SD was met; otherwise, NE
PR	CR	PR
PR	PR	PR
PR	SD	SD
PR	PD	SD, provided minimum duration for SD was met; otherwise, PD
PR	NE	SD, provided minimum duration for SD was met; otherwise, NE
NE	NE	NE

CR= complete response; NE= not evaluable; PD = progressive disease; PR = partial response;

SD= stable disease.

^a If a CR is truly met at the first timepoint, any disease seen at a subsequent timepoint, even disease meeting PR criteria relative to baseline, qualifies as PD at that point (since disease must have reappeared after CR). Best response would depend on whether the minimum duration for SD was met. However, sometimes CR may be claimed when subsequent scans suggest small lesions were likely still present and in fact the patient had PR, not CR, at the first timepoint. Under these circumstances, the original CR should be changed to PR and the best response is PR.

Special Notes on Response Assessment

When nodal disease is included in the sum of target lesions and the nodes decrease to “normal” size (< 10 mm), they may still have a measurement reported on scans. This measurement should be recorded even though the nodes are normal in order not to overstate progression should it be based on increase in size of the nodes. As noted earlier, this means that patients with CR may not have a total sum of “zero” on the CRF.

Patients with a global deterioration of health status requiring discontinuation of treatment without objective evidence of disease progression at that time should be reported as “symptomatic deterioration.” Every effort should be made to document objective progression even after discontinuation of treatment. Symptomatic deterioration is not a descriptor of an objective response; it is a reason for stopping study therapy. The objective response status of such patients is to be determined by evaluation of target and nontarget disease as shown in Table 1, Table 2, and Table 3.

For equivocal findings of progression (e.g., very small and uncertain new lesions; cystic changes or necrosis in existing lesions), treatment may continue until the next scheduled assessment. If at the next scheduled assessment progression is confirmed, the date of progression should be the earlier date when progression was suspected.

In studies for which patients with advanced disease are eligible (i.e., primary disease still or partially present), the primary tumor should also be captured as a target or nontarget lesion, as appropriate. This is to avoid an incorrect assessment of complete response if the primary tumor is still present but not evaluated as a target or nontarget lesion.

16.4 Immune-modified Response Evaluation Criteria in Solid Tumors

Conventional response criteria may not be adequate to characterize the anti-tumor activity of immunotherapeutic agents like atezolizumab, which can produce delayed responses that may be preceded by initial apparent radiological progression, including the appearance of new lesions. Therefore, immune-modified response criteria have been developed that account for the possible appearance of new lesions.

Immune-modified Response Evaluation Criteria in Solid Tumors (irRECIST) is derived from RECIST, Version 1.1 (v1.1) conventions^{1,2,3} and immune-related response criteria^{3,4,5} (irRC). When not otherwise specified, RECIST v1.1 conventions will apply.

Immune-Modified RECIST and RECIST v1.1: Summary of Changes

	RECIST v1.1	Immune-Modified RECIST
New lesions after baseline	Define progression	New measurable lesions are added into the total tumor burden and followed.
Non-target lesions	May contribute to the designation of overall progression	Contribute only in the assessment of a complete response
Radiographic progression	First instance of $\geq 20\%$ increase in the sum of diameters or unequivocal progression in non-target disease	Determined only on the basis of measurable disease

RECIST= Response Evaluation Criteria in Solid Tumors.

16.4.1 Definitions of measurable/non-measurable lesions

All measurable and non-measurable lesions should be assessed at Screening and at the protocol-specified tumor assessment timepoints. Additional assessments may be performed, as clinically indicated for suspicion of progression.

16.4.1.1 Measurable lesions

Tumor Lesions. Tumor lesions must be accurately measured in at least one dimension (longest diameter in the plane of measurement is to be recorded) with a minimum size as follows:

- 10 mm by computed tomography (CT) or magnetic resonance imaging (MRI) scan (CT/MRI scan slice thickness/interval no greater than 5 mm)

- 10-mm caliper measurement by clinical examination (lesions that cannot be accurately measured with calipers should be recorded as non-measurable)

Malignant Lymph Nodes. To be considered pathologically enlarged and measurable, a lymph node must be ≥ 15 mm in the short axis when assessed by CT scan (CT scan slice thickness recommended to be no greater than 5 mm). At baseline and follow-up, only the short axis will be measured and followed.

16.4.1.2 Non-measurable lesions

Non-measurable tumor lesions encompass small lesions (longest diameter < 10 mm or pathological lymph nodes with short axis ≥ 10 but < 15 mm), as well as truly non-measurable lesions. Lesions considered truly non-measurable include leptomeningeal disease, ascites, pleural or pericardial effusion, inflammatory breast disease, lymphangitic involvement of skin or lung, peritoneal spread, and abdominal mass/abdominal organomegaly identified by physical examination that is not measurable by reproducible imaging techniques.

16.4.1.3 SPECIAL CONSIDERATIONS REGARDING LESION MEASURABILITY

Bone lesions, cystic lesions, and lesions previously treated with local therapy require particular comment, as outlined below.

Bone Lesions

Bone scan, positron emission tomography (PET) scan, or plain films are not considered adequate imaging techniques for measuring bone lesions. However, these techniques can be used to confirm the presence or disappearance of bone lesions.

Lytic bone lesions or mixed lytic–blastic lesions, with identifiable soft tissue components, that can be evaluated by cross-sectional imaging techniques such as CT or MRI can be considered as measurable lesions if the soft tissue component meets the definition of measurability described above.

Blastic bone lesions are non-measurable.

Cystic Lesions

Lesions that meet the criteria for radiographically defined simple cysts should not be considered as malignant lesions (neither measurable nor non-measurable) since they are, by definition, simple cysts.

Cystic lesions thought to represent cystic metastases can be considered as measurable lesions, if they meet the definition of measurability described above. However, if non-cystic lesions are present in the same patient, these are preferred for selection as target lesions.

Lesions with Prior Local Treatment

Tumor lesions situated in a previously irradiated area or in an area subjected to other loco-regional therapy are usually not considered measurable unless there has been demonstrated

progression in the lesion. Study protocols should detail the conditions under which such lesions would be considered measurable.

16.4.2 Tumor response evaluation

16.4.2.1 Definitions of target/non-target lesions

Target Lesions

When more than one measurable lesion is present at baseline, all lesions up to a maximum of five lesions total (and a maximum of two lesions per organ) representative of all involved organs should be identified as target lesions and will be recorded and measured at baseline. This means that, for instances in which patients have only one or two organ sites involved, a maximum of two lesions (one site) and four lesions (two sites), respectively, will be recorded. Other lesions (albeit measurable) in those organs will be recorded as non-measurable lesions (even if the size is >10 mm by CT scan).

Target lesions should be selected on the basis of their size (lesions with the longest diameter) and be representative of all involved organs, but in addition, should lend themselves to reproducible repeated measurements. It may be the case that, on occasion, the largest lesion does not lend itself to reproducible measurement, in which circumstance, the next largest lesion that can be measured reproducibly should be selected.

Lymph nodes merit special mention since they are normal anatomical structures that may be visible by imaging even if not involved by tumor. As noted above, pathological nodes that are defined as measurable and may be identified as target lesions must meet the criterion of a short axis of ≥ 15 mm by CT scan. Only the short axis of these nodes will contribute to the baseline sum. The short axis of the node is the diameter normally used by radiologists to judge if a node is involved by solid tumor. Nodal size is normally reported as two dimensions in the plane in which the image is obtained (for CT, this is almost always the axial plane; for MRI, the plane of acquisition may be axial, sagittal, or coronal). The smaller of these measures is the short axis. For example, an abdominal node that is reported as being 20 mm \times 30 mm has a short axis of 20 mm and qualifies as a malignant, measurable node. In this example, 20 mm should be recorded as the node measurement. All other pathological nodes (those with short axis ≥ 10 mm but < 15 mm) should be considered non-target lesions. Nodes that have a short axis of < 10 mm are considered non-pathological and should not be recorded or followed.

Lesions irradiated within 3 weeks prior to Cycle 1 Day 1 may not be counted as target lesions.

Non-Target Lesions

All other lesions (or sites of disease), including pathological lymph nodes, should be identified as non-target lesions and should also be recorded at baseline. Measurements are not required.

It is possible to record multiple non-target lesions involving the same organ as a single item on the Case Report Form (CRF) (e.g., “multiple enlarged pelvic lymph nodes” or “multiple liver metastases”).

After baseline, changes in non-target lesions will contribute only in the assessment of complete response (i.e., a complete response is attained only with the complete disappearance of all tumor lesions, including non-target lesions) and will not be used to assess progressive disease.

New Lesions

During the study, all new lesions identified and recorded after baseline must be assessed at all tumor assessment timepoints. New lesions will also be evaluated for measurability with use of the same criteria applied to prospective target lesions at baseline per RECIST, (e.g., non-lymph node lesions must be $\geq 10\text{mm}$; see note for new lymph node lesions below). Up to a maximum of five new lesions total (and a maximum of two lesions per organ), all with measurements at all timepoints, can be included in the tumor response evaluation. New lesion types that would not qualify as target lesions per RECIST cannot be included in the tumor response evaluation.

New lesions that are not measurable at first appearance but meet measurability criteria at a subsequent timepoint will be measured from that point on and contribute to the sum of longest diameters (SLD), if the maximum number of 5 measurable new lesions being followed has not been reached.

16.4.2.2 Calculation of sum of the diameters

A sum of the diameters (longest for non-nodal lesions, short axis for nodal lesions) for all target lesions will be calculated as a measure of tumor burden.

The sum of the diameters is calculated at baseline and at each tumor assessment for the purpose of classification of tumor responses.

Sum of the Diameters at Baseline: The sum of the diameters for all target lesions identified at baseline prior to treatment on Day 1.

Sum of the Diameters at Tumor Assessment: For every on-study tumor assessment collected per protocol or as clinically indicated the sum of the diameters at tumor assessment will be calculated using tumor imaging scans. All target lesions selected at baseline and up to five new measurable lesions (with a maximum of two new lesions per organ) that have emerged after baseline will contribute to the sum of the diameters at tumor assessment. Hence, each net percentage change in tumor burden per assessment with use of immune-modified RECIST accounts for the size and growth kinetics of both old and new lesions as they appear.

Note: In the case of new lymph nodes, RECIST v1.1 criteria for measurability (equivalent to baseline target lesion selection) will be followed. That is, if at first appearance the short axis

of a new lymph node lesion ≥ 15 mm, it will be considered a measurable new lesion and will be tracked and included in the SLD. Thereafter, the lymph node lesion will be measured at subsequent timepoints and measurements will be included in the SLD, even if the short axis diameter decreases to < 15 mm (or even < 10 mm). However, if it subsequently decreases to < 10 mm, and all other lesions are no longer detectable (or have also decreased to a short axis diameter of < 10 mm if lymph nodes), then a response assessment of CR may be assigned.

If at first appearance the short axis of a new lymph node is ≥ 10 mm and < 15 mm, the lymph node will not be considered measurable but will still be considered a new lesion. It will not be included in the SLD unless it subsequently becomes measurable (short axis diameter ≥ 15 mm).

The appearance of new lymph nodes with diameter < 10 mm should not be considered pathological and not considered a new lesion.

16.4.2.3 Response criteria

Timepoint Response

It is assumed that at each protocol-specified timepoint, a response assessment occurs. Table 1 provides a summary of the overall response status calculation at each timepoint for patients who have measurable disease at baseline.

Complete Response (CR): Disappearance of all target and non-target lesions. Lymph nodes that shrink to < 10 mm short axis are considered normal.

Partial Response (PR): At least a 30% decrease in the sum of the diameters of all target and all new measurable lesions, taking as reference the baseline sum of diameters, in the absence of CR.

Note: The appearance of new measurable lesions is factored into the overall tumor burden, but *does not automatically qualify as progressive disease* until the sum of the diameters increases by $\geq 20\%$ when compared with the sum of the diameters at nadir.

Stable Disease (SD): Neither sufficient shrinkage to qualify for PR nor sufficient increase to qualify for PD, taking as reference the smallest sum of the diameters while on study.

Progressive Disease (PD): At least a 20% increase in the sum of diameters of all target and selected new measurable lesions, taking as reference the smallest sum on study (nadir SLD; this includes the baseline sum if that is the smallest on study). In addition to the relative increase of 20%, the sum must also demonstrate an absolute increase of at least 5 mm.

Impact of New Lesions on Immune-Modified RECIST

New lesions alone do not qualify as progressive disease. However, their contribution to total tumor burden is included in the sum of the diameters, which is used to determine the overall immune-modified RECIST tumor response.

Missing Assessments and Not Evaluable Designation

When no imaging/measurement is done at all at a particular timepoint, the patient is considered not evaluable (NE) at that timepoint. If only a subset of lesion measurements are made at an assessment, usually the case is also considered NE at that timepoint, unless a convincing argument can be made that the contribution of the individual missing lesion(s) would not change the assigned timepoint response. This would only happen in the case of PD. For example, if a patient had a baseline sum of 50 mm with three measured lesions and at follow-up only two lesions were assessed but those gave a sum of 80 mm, the patient will be assigned PD status, regardless of the contribution of the missing lesion.

Table 1 Immune-Modified RECIST Timepoint Response Definitions

% Change in Sum of the Diameters ^a	Non-Target Lesion Response Assessment	Overall Immune-Modified RECIST Timepoint Response
- 100% from baseline ^b	CR	CR
- 100% from baseline ^b	Non-CR or not all evaluated	PR
≤ - 30% from baseline	Any	PR
> - 30% to < +20%	Any	SD
Not all evaluated	Any	NE
≥ + 20% from nadir SLD	Any	PD

CR= complete response; NE= not evaluable; PD = progressive disease; PR = partial response; RECIST=Response Evaluation Criteria in Solid Tumors; SD = stable disease; SLD = sum of the longest diameter.

^a Percent change in sum of the diameters (including measurable new lesions when present).

^b When lymph nodes are included as target lesions, the % change in the sum of the diameters may not be 100% even if complete response criteria are met, since a normal lymph node is defined as having a short axis of < 10 mm. Any pathological lymph nodes (whether target or non-target) must have reduction in short axis to < 10 mm in order to meet the definition of CR.

16.5 Methods of contraception

At a minimum, subjects must agree to use one highly effective method of contraception as listed below:

HIGHLY EFFECTIVE METHODS OF CONTRACEPTION

Highly effective methods of contraception have a failure rate of < 1% when used consistently and correctly. WOCBP and female partners of male subjects, who are WOCBP, are expected to use one of the highly effective methods of contraception listed below. Male subjects must inform their female partners who are WOCBP of the contraceptive requirements of the protocol and are expected to adhere to using contraception with their partner.

For WOCBP

Highly effective methods of birth control include the following:

1. Progestogen only hormonal contraception associated with inhibition of ovulation.
2. Hormonal methods of contraception including oral contraceptive pills containing combined estrogen + progesterone, vaginal ring, injectables, implants and intrauterine devices (IUDs) such as Mirena®
3. Nonhormonal IUDs, such as ParaGard®
4. Bilateral tubal occlusion
5. Vasectomised partner with documented azoospermia 90 days after procedure
 - Vasectomised partner is a highly effective birth control method provided that partner is the sole sexual partner of the WOCBP trial participant and that the vasectomised partner has received medical assessment of the surgical success.
6. Intrauterine hormone-releasing system (IUS).
7. Complete abstinence
 - Complete Abstinence is defined as complete avoidance of heterosexual intercourse and is an acceptable form of contraception for all study drugs. This also means that abstinence is the preferred and usual lifestyle of the patient. This does not mean periodic abstinence (eg, calendar, ovulation, symptothermal, profession of abstinence for entry into a clinical trial, post-ovulation methods) and withdrawal, which are not acceptable methods of contraception. Women must continue to have pregnancy tests. Acceptable alternate methods of highly or less effective contraception's must be discussed in the event that the subject chooses to forego complete abstinence.
 - Complete abstinence is an acceptable form of contraception for all study drugs and must be used throughout the duration of the study treatment (plus 5 half-lives of the investigational drug plus 30 days).
 - It is not necessary to use any other method of contraception when complete abstinence is elected.
 - Subjects who choose complete abstinence must continue to have pregnancy tests.

- Acceptable alternate methods of highly effective contraception must be discussed in the event that the subject chooses to forego complete abstinence.
- The reliability of sexual abstinence needs to be evaluated in relation to the duration of the clinical trial and the preferred and usual lifestyle of the subject.

“MALE SUBJECTS WITH PARTNERS WHO ARE WOCBP:

Are required to use condoms, in addition to the requirement for their female partners who are WOCBP to use a highly effective method of contraception listed above.”

UNACCEPTABLE METHODS OF CONTRACEPTION

1. Periodic abstinence (calendar, symptothermal, post-ovulation methods)
2. Withdrawal (coitus interruptus)
3. Spermicide only
4. Lactation amenorrhea method (LAM)

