5.0 METHODOLOGY

5.1 Entry Criteria

5.1.1 Subject Inclusion Criteria

- Age >18 years
- Recurrent or secondary primary squamous cell carcinoma originating from the oral cavity, oro/hypo-pharynx or larynx
- Prior radiotherapy (46-70Gy)
- Adequate newly obtained core or excisional biopsy of a recurrent tumor lesion
- Measurable disease
- Lesion available for biopsy during study treatment
- Eastern Cooperative Oncology Group (ECOG) performance status of 0 or 1
- Life expectancy > 12 months
- A minimum of 6 months since prior radiotherapy in the same area or minimum 4 weeks (28 days) since previous other cancer treatment
- Both HPV positive and HPV negative disease allowed
- Distant metastases allowed
- Adequate organ function based on clinical examination and lab values
- Women of childbearing potential (WOCBP) must have a negative serum or urine pregnancy test (minimum sensitivity 25 IU/L or equivalent units of HCG) within 24 hours prior to the start of study drug
- Women must not be breastfeeding
- WOCBP should use an adequate method to avoid pregnancy for 23 weeks (30 days plus the time required for nivolumab to undergo five half-lives) after the last dose of investigational drug
- Males who are sexually active with WOCBP must agree to follow instructions for method(s) of contraception for a period of 90 days (duration of sperm turnover) plus the time required for the investigational drug to undergo five half-lives. The terminal half-life of nivolumab is up to 25 days

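### Appendix 16.5 states two different contraceptive standards for a subject who gives up complete abstinence, and one of them admits methods below the appendix's own minimum

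*Combined protocol and SAP*

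**What the plan says.** All the conflicting text is in Appendix 16.5, Methods of contraception.

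- The appendix opens with a floor: "At a minimum, subjects must agree to use one highly effective method of contraception as listed below".
- It then defines the term: "Highly effective methods of contraception have a failure rate of < 1% when used consistently and correctly".
- Complete abstinence is item 7 of the list headed for women of childbearing potential (WOCBP). Within that item, the sentence that begins "Acceptable alternate methods of highly or less effective" reads in full: "Acceptable alternate methods of highly or less effective contraception's must be discussed in the event that the subject chooses to forego complete abstinence".
- A later bullet on the same subject reads: "Acceptable alternate methods of highly effective contraception must be discussed in the event that the subject chooses to forego complete abstinence".

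The separate block for male subjects asks for condoms in addition to a highly effective method for the partner. The appendix ends with a list of four unacceptable methods. Section 5.1.1 asks WOCBP to use an adequate method, without defining adequate.

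**The concern.** A subject who elects complete abstinence meets the opening floor, because abstinence is on the list. If she later gives it up, the protocol has to say what she may move to. It says so twice, and the answers differ: one sentence includes less effective methods among the acceptable alternates, and the other does not.

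Two sites could therefore each follow a written line of the protocol and apply different standards to the same situation. The site using the wider sentence could accept a method that the opening of the appendix rules out. What is at stake is protection against pregnancy during and after exposure to the study drug. The protocol treats this as a safety matter: section 9.2 has pregnancies handled as serious adverse events, and section 9.5 requires permanent discontinuation of study drug and follow-up of the outcome.

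**Working it through.** No plan figure depends on the method standard, so the check is a comparison of the texts.

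1. **Same trigger?** Yes. Both sentences apply when the subject decides to forgo complete abstinence.

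2. **Same population?** Yes. Both belong to the bullets on abstinence, and neither is limited to a subgroup, a treatment phase or a type of site.

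3. **Same content?** No. Apart from a stray possessive, the sentences differ in one respect: one covers highly effective or less effective methods, the other highly effective methods only.

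4. **Consistent with the floor?** The floor is one highly effective method, meaning a failure rate below 1%. A method classed as less effective than that falls outside the definition. The narrower sentence is compatible with the floor. The wider sentence is not, for the part that refers to less effective methods.

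5. **Does other text settle it?**
   - Section 5.1.1 does not, because its adequate method is undefined.
   - The list of unacceptable methods does not. It names periodic abstinence, withdrawal, spermicide only and lactational amenorrhoea. A method on neither list, such as a condom used alone, is not classified there.
   - The male block concerns male subjects and their partners, and does not address a female subject who gives up abstinence.
   - No sentence says which statement prevails if they differ.

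6. **Can the effect be sized?** No. The 1% limit is given without a time unit and applies to consistent and correct use. The documents give no rate for less effective methods. They also do not say how many of the 20 subjects will be WOCBP, how many will elect abstinence, or how many will give it up.

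**The case against.** The strongest reply is that the wider sentence only requires a discussion. It does not say that a less effective method satisfies the protocol. The floor comes first and is mandatory, and the repeated bullet and the male block both ask for a highly effective method. On this view the extra words are a leftover from a near-duplicate sentence, and a careful reader would follow the floor.

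Much of this stands. The sentence does not expressly permit a substitution, and it is outnumbered within the appendix. Other safeguards also apply whichever sentence is followed: pregnancy testing every 5 cycles, and stopping study drug if pregnancy is confirmed.

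It does not remove the conflict. The sentence describes the methods to be discussed as acceptable alternates, so a site could reasonably take a less effective method as allowed. Being outnumbered does not make a current sentence inoperative, and testing detects a pregnancy without preventing one.

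**Conclusion.** The point holds as a contradiction of wording within Appendix 16.5, limited to the method standard after abstinence is given up. It bears on participant safety and leaves the endpoints, sample size, dose-escalation rule and analyses unchanged. It rests on one assumption: that a site may read acceptable alternates as permission. The number of subjects affected is unknown and may be small.

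Two stronger readings are tempting, and the documents do not support them.

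- **A shorter period for male subjects' partners.** The only duration in the appendix is the abstinence line, which runs through treatment "plus 5 half-lives of the investigational drug plus 30 days". Section 5.1.1 has sexually active men follow contraceptive instructions "for a period of 90 days (duration of sperm turnover) plus the time required for the investigational drug to undergo five half-lives". The appendix also points partners to the same list, so a reader might infer a conflict. With the half-life of up to 25 days in section 5.1.1, the abstinence line gives 5 × 25 + 30 = 155 days and the male rule gives 5 × 25 + 90 = 215 days, an apparent gap of 215 − 155 = 60 days. However, the abstinence line sits under the heading for WOCBP and matches the period for women in section 5.1.1: 155 / 7 = 22.1 weeks, which rounds up to the stated 23. The male block gives no duration that could contradict section 5.1.1. The male rule there covers men who are sexually active with WOCBP, so it is not written for a couple who remain abstinent. The 60 days arise only if a line for women is carried over to partners. At most, the appendix lacks a cross-reference.

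- **A numerical pregnancy risk.** A reader might want to set a cumulative failure rate under the wider sentence against one under the floor. Any rate for less effective methods would have to come from outside the documents, so no such figure is given here.

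**What to change.** Reconcile the two sentences on giving up abstinence with each other and with the opening minimum of Appendix 16.5, so that the appendix states one method standard, once. Which standard applies is a clinical decision for the sponsor and is not proposed here. If the consent text repeats the wording, align it. As an optional addition, the male block could refer to the period already set in section 5.1.1 (five half-lives plus 90 days), so that both method and period can be found from one place.

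The cost is a wording change in the appendix and, where needed, in the consent form. No visit, procedure or analysis is added.
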